7.3 Eligibility Criteria

A staged enrolment process will be used to identify patients eligible to be enrolled and randomized in the study. At each stage of the enrolment process, a patient must meet inclusion criteria and not meet exclusion criteria in order to pass. To progress to the next stage, patients must continue to pass criteria from the prior stages. After enrolment, there are also specific tests to perform (with pass/fail criteria) to determine eligibility to be randomized. The five stages (sets of criteria and tests) are:

A. Screening Criteria

B. Enrolment Criteria and Obtaining Consent

C. Pressure Support Trial Criteria and the Pressure Support Trial

D. Weaning Criteria and the CPAP Trial and the Spontaneous Breathing Trial (SBT)

E. Randomization Criteria

The first stage of enrolment is called (A) **Screening**. Patients are screened while they are in the acute phase of their respiratory failure.

To be considered eligible for Screening, a participant must satisfy each of the following inclusion criteria:

A. Screening Inclusion Criteria:

A1.	Age ≥18 years
A2.	Intubated and receiving any mode of invasive MV ≥24 hours

All patients admitted to a participating site ICU during the study period meeting the above screening inclusion criteria will be entered into a screening log and followed until they satisfy all inclusion criteria, are enrolled and randomized, or meet an exclusion criterion and exit the screening/enrolment process.

A participant will be ineligible for participation in this study and will be counted as a “screen failure” if he or she satisfies any one or more of the following exclusion criteria:

A. Screening Exclusion Criteria:

A3	Anticipating withdrawal of life support and/or shift to palliation as the goal of care
A4	Severe central neurologic disorder (eg. Hemorrhage, stroke, tumour) causing elevated intracranial pressure, or impaired control of breathing, or requiring specific ventilator adjustments (i.e. To attain specific CO ₂ target) or requiring neurosurgical intervention
A5	Known or suspected severe or progressive neuromuscular disorder likely to result in prolonged or chronic ventilator dependence (eg. Guillain-Barré syndrome, Myasthenia Gravis, ALS, MS, high spinal cord injury, kyphoscoliosis, or other restrictive disorder) (Note that obesity hypoventilation syndrome that may be managed with nocturnal non-invasive ventilation is NOT an exclusion under A5)

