A6	Severe COPD: Baseline daytime hypercapnea (pCO ₂ > 50 mmHg) OR GOLD 4 airflow limitation (FEV ₁ <30% predicted) OR MRC class 4 symptoms (“I am too breathless to leave the house” OR “I am breathless when dressing”)
A7	Broncho-pleural fistula
A8	Tracheostomy present at ICU admission for the purpose of chronic or prolonged mechanical ventilation (>21 days). (Note that a patient who was endotracheally intubated for acute respiratory failure and received a tracheostomy during their ICU admission, prior to enrolment, is not excluded under A8).
A9	Current enrolment in a confounding study, as assessed by the steering committee
A10	Previous randomization in the PROMIZING Study
A11	Severe, end-stage, irreversible respiratory or cardiac disease (e.g. interstitial lung disease, pulmonary fibrosis, cardiomyopathy, valvulopathy) likely to result in prolonged or chronic ventilator dependence /unlikely to wean from mechanical ventilation [Note: patients who are candidates for intervention to treat the underlying respiratory/cardiac disease (e.g. lung transplant, heart transplant, cardiac surgery) may be re-evaluated once intervention is complete and they no longer meet criteria A11.]

Patients satisfying all of the Screening inclusion criteria and none of the Screening exclusion criteria will be classified as “eligible” and will be followed daily until they meet **all** of the following criteria to be approached for consent. This is the second stage, called **(B) Enrolment and Obtaining Consent**, and it occurs as the patient approaches the “recovery phase” of his/her critical illness, as defined by passing the “Enrolment Inclusion Criteria” listed below.

B. Enrolment Inclusion Criteria:

B1.	Ability or potential ability to trigger ventilator breaths (i.e. not receiving neuromuscular blockade).
B2.	On Assist/Control volume-cycled ventilation: Technically satisfactory plateau pressure ≤ 30 cm H ₂ O (see Operations Manual) OR On Assist/Control pressure-controlled ventilation or similar mode: Pressure control plus PEEP ≤ 30 cm H ₂ O OR On Pressure Support ventilation: Pressure support plus PEEP ≤ 30 cm H ₂ O OR On Proportional Assist ventilation: PAV gain <85%
B3.	PaO ₂ ≥ 60 mmHg or SpO ₂ ≥ 90% on FiO ₂ ≤ 0.60 and PEEP ≤ 15 cm H ₂ O
B4.	Metabolic disorders corrected: pH ≥7.32

B5.	Stable hemodynamic status: stable or decreasing doses of vasopressors for ≥ 6 hours
B6.	Anticipate ongoing need for ventilation > 24 hours

B. Enrolment Deferral Criteria:

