4.1 Eligibility Criteria

We will include critically ill adult patients (age \geq 18 years) receiving invasive MV for ARF for at least 24 hours, and judged ready to commence, and be maintained with, partial ventilatory support (tolerating PSV

for at least 30 minutes) (20) but not yet ready for extubation (not yet ready for a spontaneous breathing trial (SBT) or having failed an SBT). The initial screening criteria will include critically ill patients who are:

- A1. Adult patients ≥ 18 years
- A2. Intubated, or tracheostomized, receiving invasive ventilation ≥ 24 hours

And will exclude patients who meet one or more of the following Screening Exclusion Criteria:

- A3. Anticipating withdrawal of life suport and/or shift to palliation
- A4. Severe central neurologic disorder
- A5. Known or suspected severe or progressive neuromuscular disorder
- A6. Severe COPD
- A7. Broncho-pleural fistula
- A8. Tracheostomy present at ICU admission for prolonged MV (>21 days)
- A9. Current enrolment in a confounding study
- A10. Previous randomization in the PROMIZING Study
- A11. Severe, end-stage, irreversible respiratory or cardiac disease

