4.6.1 Intention To Treat Sample

All analyses will use the intention to treat sample. The intention to treat sample will be comprised of all randomized patients who started the study intervention, irrespective of compliance to their randomized group. Patients will contribute outcome data to the analysis based on the randomized group.

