5.2 Secondary Outcomes

The secondary outcomes are

- 1. Ventilator-free days at day 14, 21 and 28 post randomization
- 2. Time from randomization to live ICU discharge (up to day 90)
- 3. Time from randomization to live hospital discharge (up to day 90)
- 4. Mortality, measured as time to death, ICU mortality; hospital mortality; 21, 28, and 90 day mortality
- 5. Weaning Progress, measured as time from randomization to: first SBT; first successful SBT; first extubation or equivalent for tracheostomized patients.
- 6. Weaning Difficulties: Subjects will be classified in the 5 following groups according the WEAN Safe classification (calculated as time from first SBT/extubation):
 - (a) Successful liberation less than 24 hrs
 - (b) Successful liberation greater than 24 hrs but less than 7 days
 - (c) Successful liberation greater than 7 days
 - (d) Unsuccessful liberation alive but remain ventilator dependent at day 90
 - (e) Died prior to successful liberation
- 7. Weaning Complications, measured as the number of patients
 - used non-invasive ventilation post-extubation
 - ventilated more than 7 days post randomization
 - ventilated more than 21 days from time of randomization
 - ventilated more than 21 days from time of intubation (prolonged MV group)
 - receiving tracheostomy post-randomization
 - requiring re-intubation (up to 7d after planned extubation)
- 8. Safety and Tolerance of modes
 - Number of patients ever requiring A/C mode post randomization
 - Number of patient-days requiring A/C mode post randomization
 - Frequency and severity of reported serious adverse events across groups
- 9. Co-interventions are also monitored, including sedatives and anti-psychotic medications.

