- Number of patients successfully liberated in less than 24 hours since first SBT or first extubation attempt, number successfully liberated greater than 24 hours but less than 7 days, successfully liberated greater than 7 days, unsuccessful liberation (alive but remaining ventilator dependent at day 90), died prior to successful liberation. These outcomes will be compared across groups using the Chi-Square or Fisher's exact test.
- Delirium and sedation scores: Daily sedation scores will be analyzed as described in Section 5.5.2.
- Number of patients who received non-invasive ventilation post-extubation, ventilated more than 7 days post randomization, ventilated more than 21 days from time of intubation (prolonged MV group); receiving tracheostomy post-randomization, requiring re-intubation (up to 7d after planned extubation): These outcomes will be compared across groups using the Chi-Square or Fisher's exact test.
- Number of patients ever receiving A/C mode post randomization (Tolerance of modes): This outcome will be compared across treatment groups using Chi-Square or Fisher's Exact test and treatment differences will be reported as an odds ratio with 95% confidence interval. Patients not receiving A/C will be assigned a value of zero days. The non-parametric Wilcoxon rank-sum test will be favoured over the parametric t-test for this analysis if there are many zero days entries.

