6.5 Subgroup Analyses

There are 4 planned subgroup analyses testing whether the trajectory of baseline characteristics can influence the results. These will be based on:

- 1. Duration of MV prior to randomization as a continuous variable modeled with restricted cubic splines if necessary to account for potentially nonlinear effects.
- 2. Status of weaning attempts prior to randomization
 - Failed SBT prior to randomization
 - Failed CPAP (of zero cmH2O) trial prior to randomization
 - Failed weaning criteria prior to randomization
- 3. Failed extubation prior to randomization
- 4. Frailty (mild/ moderate/ severe)

In addition, we will explore the possibility of a subgroup analysi by covid status at randomization if there are enough COVID+ subjects. COVID+ will be defined as COVID+ and a respiratory diagnosis

- 1. COVID positivity at randomization (due to the onset of the pandemic)
- 2. tracheostomy prior to randomization

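### The count of patients ventilated more than 21 days from intubation includes patients already past day 21 at randomization, which dilutes the comparison between arms

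*SAP*

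**What the plan says.** - **Outcomes and test.** SAP 6.2 lists among the weaning complications the number of patients "ventilated more than 21 days from time of intubation (prolonged MV group); receiving tracheostomy post-randomization". The same bullet ends "requiring re-intubation (up to 7d after planned extubation): These outcomes will be compared across groups using the Chi-Square or Fisher's exact test". It states no at-risk denominator and no baseline adjustment.
- **Denominator.** SAP 4.6.1: "All analyses will use the intention to treat sample".
- **Prior ventilation.** Protocol 7.3, criterion A2, requires "Intubated and receiving any mode of invasive MV ≥24 hours" and gives no upper limit. The more-than-21-days wording in criterion A8 concerns only a tracheostomy already present at ICU admission. Exclusion B9 limits time on tolerated partial support, not total ventilation. Enrolment can wait for ECMO or surgery to end, and the pressure support trial can be deferred day by day, so late randomization is possible.
- **Prior tracheostomy.** The note to A8 says that a patient who "received a tracheostomy during their ICU admission, prior to enrolment, is not excluded under A8". SAP 4.1 describes eligible patients as "Intubated, or tracheostomized, receiving invasive ventilation" and SAP 6.5 lists "tracheostomy prior to randomization" as an exploratory subgroup.
- **Companion outcome.** SAP 5.2 also lists "ventilated more than 21 days from time of randomization". The analysis list in SAP 6.2 omits it.

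**The concern.** A patient randomized on, say, day 25 of ventilation is scored as a prolonged-ventilation complication before the assigned mode has been used. Adding the same block of certain events to both arms moves the risk ratio and odds ratio toward 1, shrinks the risk difference, and raises the reported complication rate with events that preceded treatment. The version of the outcome that avoids this has been defined but has no stated analysis.

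Tracheostomy has the mirror-image problem. Patients who already have one cannot have the event but stay in the denominator, so the reported rate and the risk difference are too small.

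At stake is the interpretation of two secondary outcomes. The primary analysis is not affected.

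**Working it through.** **The plan's own figure.** At hazard ratio (HR) 1.30, events = 4(1.960 + 0.842)²/(ln 1.30)² = 456.1; the documents state 456. Then 529/0.95 = 556.8, so 557, or 558 as an even total. These reproduce and do not depend on the present point.

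**Inputs for the 21-day outcome**
- Median times to liberation 7.70 (PSV) and 5.92 (PAV+) days, with exponential times (Protocol 12.1). Hazards: ln 2/7.70 = 0.0900 and ln 2/5.92 = 0.1171 per day.
- The death hazard is not given. Taking it equal in the arms and solving ½[0.0900/(0.0900 + δ) + 0.1171/(0.1171 + δ)] = 456/529 gives δ = 0.0163 per day.
- Ventilation before randomization, X, is not described apart from the 5-day subgroup cut. Assumption: lognormal, median 4-6 days, log-SD 0.8-1.0, minimum 1 day.
- 279 patients per arm, two-sided 5%.

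**Formulas**
- Share already past day 21: f = P(X > 21).
- Risk among the rest: q = mean of exp[−(λ + δ)(21 − X)] over X ≤ 21, where λ is the arm's liberation hazard. A death before day 21 is not an event.
- Risk as written: f + (1 − f)q.

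| Median, log-SD | f | At risk, PSV v PAV+ | Risk ratio | As written, PSV v PAV+ | Risk ratio | Power: at risk / as written |
|---|---|---|---|---|---|---|
| 4, 0.8 | 1.9% | 20.3% v 14.1% | 0.69 | 21.8% v 15.7% | 0.72 | 48.6% / 45.3% |
| 5, 0.9 | 5.5% | 23.2% v 16.9% | 0.73 | 27.5% v 21.5% | 0.78 | 44.5% / 37.8% |
| 6, 1.0 | 10.5% | 25.4% v 18.9% | 0.75 | 33.2% v 27.5% | 0.83 | 40.8% / 31.4% |

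Check of the last row: 0.1051 + 0.8949 × 0.2536 = 0.332 and 0.1051 + 0.8949 × 0.1894 = 0.275; ratio 0.83. Patients already past day 21 make up f/risk = 9-32% of the PSV events and 12-38% of the PAV+ events.

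**A second set of assumptions.** With at-risk rates of 30% v 20% and f = 10%, the rates become 0.10 + 0.90 × 0.30 = 37.0% and 0.10 + 0.90 × 0.20 = 28.0%. The odds ratio falls from 1.71 to 1.51. Power is 62% as written and 74% in the at-risk patients.

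**Bias.** With equal at-risk rates of 25%, simulated type I error was 5.1% both with f = 0 and with f = 10%.

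**Tracheostomy.** With a share g already tracheostomized, both rates are multiplied by (1 − g). At 30% v 20% (assumed) and g = 10%, they become 27% v 18%. The risk ratio stays at 1.50, the odds ratio moves from 1.71 to 1.69, and the risk difference goes from 10 to 9 points. Power as written v restricted is 75.2% v 75.9% at g = 5%, 72% v 74% at g = 10%, and 65.7% v 68.5% at g = 20%.

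**The case against.** The strongest reply is that this matters little.

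- **Randomization balances prior state on average.** This stands: there is no bias between arms. Stratification is by site only, so a chance imbalance remains possible.
- **The rest of the plan measures ventilation from randomization.** This also stands. The primary outcome, ventilator-free days at 14, 21 and 28 days, and the count ventilated more than 7 days after randomization all start at randomization. A reader might infer that the trial could miss a real reduction in prolonged ventilation. The documents do not support that. The 21-day count has less than 50% power under the first set of assumptions even when restricted, so dilution is not the main reason that it could be negative.
- **Counting from intubation is the stated definition of the prolonged-ventilation group.** This stands. A patient intubated 20 days before randomization and liberated 1.5 days later still counts after the restriction (20 + 1.5 = 21.5 days). The restriction removes only patients whose result was already fixed; the from-randomization outcome answers the separate question of time origin.
- **Weaning outcomes are viewed mainly descriptively.** This holds only in part. The opening sentence of SAP 6.2 names weaning progress and difficulties, while complications are given a test. SAP 3.1 promises an estimate, interval and p-value for every outcome analysed. A descriptive rate would still mix events from before and after randomization.
- **Prior ventilation is a covariate and subgroup variable, and prior tracheostomy an exploratory subgroup.** True, but neither is tied to these two outcomes.

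**Conclusion.** The point holds as one of dilution in a secondary outcome. As written, the from-intubation count includes automatic events in both arms. If 2-11% of patients are past day 21 at randomization, the risk ratio moves from 0.69-0.75 to 0.72-0.83 and power from about 41-49% to 31-45%. These figures rest on an assumed distribution of prior ventilation and an inferred death hazard; the documents give neither. That the from-randomization outcome has no stated analysis in SAP 6.2 needs no assumption.

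The tracheostomy part is minor. The event rate and risk difference are understated by the baseline share, the risk ratio does not change, and restriction recovers about 1-3 points of power. A reader might infer that a real reduction in tracheostomies could be missed; the numbers do not support that.

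Nor should the risk ratio for more than 21 days from randomization, exp(−21 × 0.1334)/exp(−21 × 0.1064) = 0.061/0.107 = 0.57, be set against the from-intubation figures as a measure of dilution. It belongs to a different outcome with a different time origin.

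**What to change.** In SAP 6.2:

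1. Restrict the count ventilated more than 21 days from intubation to patients ventilated 21 days or less at randomization. State which intubation starts the clock, since extubation may have failed before randomization.
2. Add the count ventilated more than 21 days from randomization, already listed in SAP 5.2, to the outcomes tested.
3. Report by arm how many patients were past day 21 at randomization.
4. Count new tracheostomy among patients without a tracheostomy at randomization.

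Both restrictions use only the patient's state at randomization, so the randomized comparison is preserved. Protocol 9.2 already tracks intubations and extubations from hospital admission, so no new data should be needed. The cost is SAP wording and slightly smaller denominators for two secondary outcomes.

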6.3 Exploratory Outcomes

Status at 90 days is an ordinal outcome defined in section 2.3.1 and it will be analyzed using ordinal logistic regression.

Exploratory analyses will include regression analyses to assess factors potentially associated with weaning group classification (short/difficult/prolonged weaning groups) and with duration of mechanical ventilation.

6.4 Covariates of Interest

The following were pre-specified as covariates are of particular interest

- 1. Duration of mechanical ventilation prior to randomization in 1) days and 2) as a binary indicator for greater than 5 days or not.
- 2. 2. Failed spontaneous breathing trial (SBT) vs. failed continuous positive airway pressure (CPAP) zero trial (CPAP trial of 0 cmH2O) vs. failed weaning criteria prior to randomization
- 3. Failed extubation prior to randomization (Failed extubation vs. No extubation attempt prior to randomization)
- 4. Mild, moderate, severe frailty assessed using the Clinical Frailty Scale (CFS) [30]. There should not be anyone with CFS 9 (Terminally ill) in the study based on the inclusion criteria

- Mild: CFS 1 to 3 (very fit to managing well)
- Moderate: CFS 4 to 6 (managing well to mildly frail)
- Severe: CFS 7 to 8 (severely frail to very severely frail)

In addition to the above pre-specified covariates, we will explore the effects of baseline cumulative fluid balance and baseline sedation category in adjusted analyses. In addition, baseline use of antipsychotics, neuromuscular blockers and steroids will be described.

6.5 Subgroup Analyses

There are 4 planned subgroup analyses testing whether the trajectory of baseline characteristics can influence the results. These will be based on:

- 1. Duration of MV prior to randomization as a continuous variable modeled with restricted cubic splines if necessary to account for potentially nonlinear effects.
- 2. Status of weaning attempts prior to randomization
 - Failed SBT prior to randomization
 - Failed CPAP (of zero cmH2O) trial prior to randomization
 - Failed weaning criteria prior to randomization
- 3. Failed extubation prior to randomization
- 4. Frailty (mild/ moderate/ severe)

In addition, we will explore the possibility of a subgroup analysi by covid status at randomization if there are enough COVID+ subjects. COVID+ will be defined as COVID+ and a respiratory diagnosis

- 1. COVID positivity at randomization (due to the onset of the pandemic)
- 2. tracheostomy prior to randomization

6.6 Sensitivity Analyses

There are 2 planned sensitivity analyses based on:

- 1. Defining "successful extubation" as "48 hours without reintubation"
- 2. Assigning a value of 0 ventilator-free days to any participant who dies at any time during the study period.

7 Bayesian Analyses

The Bayesian analyses will be performed by [name], under the supervision of Drs. [name] and [name]. The goal of this analysis is to incorporate prior evidence into the analysis of the PROMIZING study. We will analyze the outcomes: time to liberation (in ICU) from mechanical ventilation and ventilator-free days. The analyses will be performed adjusted by the covariates of interest (section 3). Posterior mean, median, and 95% highest density credible intervals will be reported for all model parameters. The probability that the treatment reduces time on ventilation by the minimal clinically important difference (MCID) of 1 day will also be reported.

7.1 Informative Prior Treatment Distributions

Our analyses will incorporate prior information from a pragmatic meta-analysis [31]. Saunders et al. reported that compared to PSV, PAV+ reduced duration on ventilation by 1.53 days (95% confidence interval: 0.83 to 2.24). The meta-analysis estimate will be weighted to 100%, 50%, and 10% to calculate prior distributions,

according to the approach in Goligher et al. [32]. Ventilator-free day data from the iCORE dataset were transformed to determine the priors for treatment effects specific to each outcome [33]. The iCORE dataset reports the number of days a patient is off ventilator within 28 days, in patients who have received PSV.

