2.1 Trial design

The PROMIZING study is a multi-centre, randomized, parallel assignment, open label clinical trial designed with a superiority framework. Neither the clinical team nor the study investigators will be blinded to the study intervention. The study statistician will be blind to the study arm. Allocation ratio is 1:1 to the two arms of the study. Patients randomized to the PAV+ intervention arm will follow a PAV+ ventilation protocol, where PAV+ is set to maintain respiratory muscle pressure within a target range of 5-10 cmH2O. Patients randomized to the PSV control arm will follow a PSV ventilation protocol, where PSV is set to maintain usual clinical parameters of respiratory rate and tidal volume. In both arms, patients who are not tolerating the assigned mode will be placed on assist/control ventilation, and in both arms, patients will undergo daily screening for readiness for liberation with protocolized spontaneous breathing trials.

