2.3 Sample Size

Sample size was calculated based on the primary outcome of time to first successful liberation from mechanical ventilation. The calculation treated death as a censoring event. Sample sizes assuming a hazard ratio ranging between 1.2 to 1.3 were calculated. We used 80% power and a 2-sided type I error of 5%. We also assumed a 5% rate of dropout.

As planned a priori, aggregate blinded data from the first 120 patients was used to re-estimate the sample size. Median time to successful liberation in the entire cohort was 6.8 days. The minimal clinically important difference was deemed to be 1 day. Assuming a hazard ratio of 1.3, to demonstrate a reduction in the median

duration of ventilation by 1.78 days, we will require 529 patients or 558 patients if we assume a loss to followup of 5%. Assuming a hazard ratio of 1.25 will require 770 patients to demonstrate a difference of 1.5 days (Table xx). We expect to enroll a minimum of 558 patients within the planned 5 year of enrollment.

Median Time (PSV)	Median Time (PAV)	Difference	Hazard Ratio	Required Events	Total N	Total N(5% lost)
7.40	6.17	1.23	1.20	944	1095	1153
7.40	5.92	1.48	1.25	630	729	768
7.40	5.69	1.71	1.30	456	526	554
7.50	6.25	1.25	1.20	944	1097	1155
7.50	6.00	1.50	1.25	630	731	770
7.50	5.77	1.73	1.30	456	527	555
7.55	6.29	1.26	1.20	944	1098	1156
7.55	6.04	1.51	1.25	630	731	770
7.55	5.81	1.74	1.30	456	528	556
7.60	6.33	1.27	1.20	944	1098	1157
7.60	6.08	1.52	1.25	630	731	771
7.60	5.85	1.75	1.30	456	528	556
7.70	6.42	1.28	1.20	944	1101	1159
7.70	6.76	1.54	1.25	630	733	772
7.70	5.92	1.78	1.30	456	529	557

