7.2 Bayesian Analysis of Primary Outcome

The primary outcome (time to successful liberation, in ICU from mechanical ventilation) will be analyzed using accelerated failure time (AFT) models. These differ from the proportional hazards models that will be used in the primary frequentist analysis (section 5.6.1) because they require distributional assumptions for the hazards. AFT models are better suited to this context because Bayesian methods assume that all parameters have a distribution. These models will estimate time ratios, which can be interpreted as the multiplicative effect of a covariate on survival time.

As specified in the primary frequentist analysis, each transition in Figure 3 will be modelled. To maximize model flexibility, each transition will be fit to a separate AFT distribution [34]. For each transition, we will select the best model among exponential and Weibull AFT families. The model with the lowest AIC will then be modeled in INLA [35, 36].

Semi-Markov modelling will be implemented, based on clinical knowledge that the probability of transitioning would depend on the time spent in each state. For these models, time will reset to 0 when patients enter each new state.

7.2.1 Informative Prior Treatment Distribution for the Transition Between Invasive Ventilation to Liberated, In ICU

We will use an informative prior for the treatment effect on the transition between invasive ventilation to liberation, in ICU. To determine the prior, we assumed that the number of ventilator-free days in the baseline dataset would roughly correspond to the time that patients were freed from ventilation. Patients with 28 ventilator-free days were considered freed on day 0. These patients were assigned a time of 0.001, as only non-zero times could be included in AFT models. For patients with 1 to 27 ventilator-free days, the difference between 28 days and the number of ventilator-free days was considered the time to being freed from ventilation. Patients who died or started off-ventilator were excluded.

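### Every weight of the informative Bayesian prior keeps the same mean favouring PAV+, and no null-centred reference prior is planned, so the full-weight interval would exclude no effect even on exactly null data

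*SAP*

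**What the plan says.** SAP section 1.3.2 says that the primary and secondary research questions will be answered with both frequentist and Bayesian methods. Section 6.1.1 makes the frequentist multistate Cox model the primary analysis.

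Section 7.1 takes the Bayesian prior from a published meta-analysis in which "PAV+ reduced duration on ventilation by 1.53 days (95% confidence interval: 0.83 to 2.24". It then says: "The meta-analysis estimate will be weighted to 100%, 50%, and 10% to calculate prior distributions".

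The tables in sections 7.2.1 and 7.3 give one mean and three SDs (100%, 50%, 10% weight) per model:

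| Model | Mean | SD 100% | SD 50% | SD 10% | MCID |
|---|---|---|---|---|---|
| Exponential, log time ratio | -0.26 | 0.074 | 0.10 | 0.23 | -0.16 |
| Weibull, log time ratio | -0.15 | 0.051 | 0.73 | 0.16 | -0.098 |
| Ventilator-free days at 28, log odds ratio | 0.25 | 0.060 | 0.085 | 0.19 | 0.17 |

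Negative time ratios and positive odds ratios favour PAV+. On the scale of the accelerated failure time (AFT) models, section 7.2 says: "These models will estimate time ratios, which can be interpreted as the multiplicative effect of a covariate on survival time". Section 7.2.1 allows a minimally informative treatment prior for the liberation transition only if some family fits substantially better than the exponential and the Weibull. Section 7.3 names no such alternative for ventilator-free days.

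The outputs listed at the start of section 7 are posterior means, medians, 95% highest density intervals and one probability: "The probability that the treatment reduces time on ventilation by the minimal clinically important difference (MCID) of 1 day".

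**The concern.** Down-weighting a prior is usually meant to show how far the answer depends on it. Here it widens the prior without moving it towards no effect. Before any data, the exponential prior puts 99.98%, 99.5% and 87% of its mass on benefit at 100%, 50% and 10% weight. Even the most discounted version is not neutral.

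If the full-weight prior also holds more information than the trial, the Bayesian section could show an interval excluding no effect when the trial found none. The reader would have no posterior on the same scale showing how much of that came from the prior. Because section 1.3.2 lets the Bayesian analysis address the primary question, such a result would carry weight.

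**Working it through.** **Inputs.** Design: "We used 80% power and a 2-sided type I error of 5" per cent (SAP 2.3), and "Allocation ratio is 1:1 to the two arms of the study" (SAP 2.1). The design row with hazard ratio 1.30 reads "7.70 5.92 1.78 1.30 456 529 557", that is, 456 events. Prior means, SDs and MCIDs are from the table above.

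**Step 1: the plan's event count.** Schoenfeld: 4 x (1.960 + 0.842)^2 / (ln 1.30)^2 = 456.1, against 456 stated. Reproduced.

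**Step 2: how the weights work.** SD at weight w = SD at 100% / sqrt(w), mean unchanged.
- Exponential: 0.074 x sqrt(2) = 0.105 and 0.074 x sqrt(10) = 0.234 (printed 0.10 and 0.23).
- Ventilator-free days: 0.085 and 0.190 (printed 0.085 and 0.19).
- Weibull at 10%: 0.051 x sqrt(10) = 0.161 (printed 0.16).
- Weibull at 50%: 0.051 x sqrt(2) = 0.072, but 0.73 is printed. This is the only mismatch and looks like a decimal slip. Taken literally, it makes that prior almost flat.

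**Step 3: information in the trial.** For the exponential model, SE = sqrt(4/456) = 0.0937, so the data precision is 114.0. For the Weibull the SE is multiplied by the scale parameter, which is unknown for this trial; I assume 1 and vary it.

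**Step 4: information in the prior.** Precision = 1/SD^2; equivalent events = 4/SD^2 (exponential).
- 100%: precision 182.6, about 730 events, 182.6/(182.6 + 114.0) = 62% of the posterior information.
- 50%: about 400 events from the rounded SD (365 is half of 730).
- 10%: about 76 events.

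**Step 5: posterior when the observed log time ratio is exactly 0.** Mean = prior mean x prior share; SD = 1/sqrt(sum of precisions).

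| Exponential, 456 events | Posterior mean (SD) | 95% interval | P(at least MCID) | P(any benefit) |
|---|---|---|---|---|
| 100% | -0.160 (0.058) | -0.274 to -0.046 | 50% | 99.7% |
| 50% | -0.121 (0.068) | -0.255 to 0.012 | 29% | 96% |
| 10% | -0.037 (0.087) | -0.207 to 0.133 | 8% | 67% |
| Flat | 0 (0.094) | -0.184 to 0.184 | 4% | 50% |

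Weibull at full weight, assumed scale 1: precision 384.5 against 114.0, mean -0.116 (SD 0.045), interval about -0.20 to -0.03. P(at least MCID) is 65% against 15% flat, and P(any benefit) is about 99.5%.

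**Step 6: sensitivity.**
- Exponential with 630 events (the requirement for hazard ratio 1.25): the full-weight prior still leads, 182.6 against 157.5, and the interval is -0.246 to -0.033.
- Weibull over assumed scales 0.7 to 1.6: P(any benefit) at full weight runs from 99.0% to 99.7%. At scale 0.7 the prior still leads, 384.5 against 232.7, and the interval is -0.172 to -0.015.
- Ventilator-free days, assuming an SE of about 0.15 on the log odds scale: P(at least MCID) on null data is about 80% at full weight against 13% flat.

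**The case against.** The Bayesian analysis is not primary, and its declared purpose is to bring in prior evidence, so a prior favouring PAV+ is intended. The data alone are shown by the Cox hazard ratio and its confidence interval, with a cause-specific Cox model beside it (SAP 6.1.1 and 6.1.2). The 10% weight is a real discount: 76 events against 456, with an MCID probability of 8% against 4%. A reader who sees 50%, 29% and 8% side by side would notice the pull of the prior.

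Much of this stands, and it limits the point to a missing reference row. It does not remove it: a Cox hazard ratio does not tell the reader what the data alone imply for an AFT time ratio or for the MCID probability.

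A reader might also infer that a null trial would be reported as a 99.7% probability of benefit. The documents do not support that. Section 7 lists no probability of any benefit; the probability it does list would be about 50% in that case. The 99.7% is only implied by the posterior and belongs to the exponential family at full weight. The baseline AIC in section 7.2.1 favours the Weibull (8625.836 against 10434.87), for which the figure is about 99.5% at scale 1.

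**Conclusion.** The point holds as a gap in the planned Bayesian reporting and should be fixed; it does not threaten the primary analysis. All three weights share one mean favouring PAV+, and no null-centred reference is planned beyond the model-fit fallback. The full-weight prior outweighs the planned trial, by about 730 events to 456 for the exponential family. On the SAP's own listed outputs, exactly null data would give a full-weight interval excluding no effect, and the prior alone would raise the MCID probability from 4% to 50% (exponential) or from 15% to 65% (Weibull, scale 1). At 50% and 10% weight the exponential interval includes no effect.

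These figures rest on a normal approximation, an unadjusted treatment effect (the SAP adjusts for covariates), all 456 events falling on the ventilation-to-liberation transition, and an assumed Weibull scale. The ventilator-free-day figure also rests on an assumed SE.

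**What to change.** - For both Bayesian outcomes, pre-specify a run with a minimally informative treatment prior centred on 0 and report it first as the reference.
- Keep the 100%, 50% and 10% weights as a sensitivity range around the meta-analytic evidence.
- State what each prior is worth in equivalent events (for ventilator-free days, its share of the posterior information).
- Recheck the printed Weibull 50% SD of 0.73 against 0.072.
- Optional: add a sceptical prior centred on 0. An SD of ln(1.30)/1.645 = 0.16 gives 5% prior probability to an effect at least as large as the design hazard ratio, but only for the exponential family. For the Weibull it must be multiplied by the scale.

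The cost is one extra run per outcome and a few table rows. The downside for the sponsor is that the leading Bayesian figure may be less favourable. The change should be made before unblinding, since a reference prior added afterwards could look driven by the results.
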